## 4 RESEARCH QUESTION AND OBJECTIVES

The primary objective of this study is to estimate the incidence of the select medical events of interest, those being the 8 System Organ Classes (SOCs) and 3 Standardized MedDRA Queries (SMQs) listed below, in pediatric patients after treatment with higher IV LCM doses, compared to pediatric patients treated with recommended initial/maintenance IV LCM dose:

- Cardiac disorders

- 
- Skin and subcutaneous tissue disorders
  - Nervous system disorders
  - Metabolism and nutrition disorders
  - Psychiatric disorders
  - Injury, poisoning and procedural complications
  - General disorders and administration site conditions
  - Investigations of ECG indicating long PR
  - Drug reaction with eosinophilia and systemic symptoms syndrome
  - Severe cutaneous adverse reactions
  - Hypersensitivity

The secondary objectives of this study are:

1. To estimate the incidence of the selected medical events included in the 8 System Organ Classes (SOC) and 3 Standardized MedDRA Queries (SMQs) as indicated below, in pediatric patients after treatment with higher than the recommended IV LCM doses, compared to pediatric patients treated with recommended initial/maintenance IV LCM dose.
- Cardiac disorders
    - Atrioventricular block
    - Atrioventricular block complete
    - Atrioventricular block first degree
    - Atrioventricular block second degree
    - Arrhythmia
    - Bradyarrhythmia
    - Bradycardia
    - Cardiac fibrillation
    - Cardiac flutter
    - Tachyarrhythmia
    - Atrial fibrillation
    - Atrial flutter
    - Cardiac arrest
    - Torsade de pointes
    - Ventricular arrhythmia
    - Ventricular fibrillation
    - Ventricular tachyarrhythmia
    - Palpitations
  - Skin and subcutaneous tissue disorders
    - Stevens-Johnson syndrome
    - Toxic epidermal necrolysis
    - Angioedema
    - Urticaria

- Pruritus
  - Rash
  - Nervous system disorders
    - Dizziness
    - Somnolence
    - Paresthesias
    - Loss of consciousness
    - Syncope
  - Metabolism and nutrition disorders
    - Appetite disorder
    - Decreased appetite
    - Diet refusal
    - Hypophagia
    - Food aversion
  - General disorders and administration site conditions
    - Chest pain
    - Gait disturbances
  - Injury, poisoning and procedural complication
    - Injection site discomfort
    - Injection site erythema
    - Injection site irritation
    - Injection site pain
2. To estimate the effect of increasing IV LCM loading dose on the incidence of select medical events for 8 SOCs and 3 SMQ terms (listed in the primary objective), compared to pediatric patients treated with recommended initial/maintenance IV LCM dose.

## 5 METHODOLOGY

### 5.1 Study design

This will be a retrospective cohort study that will use data from the PEDSnet database to estimate the incidence of select medical events for 8 SOCs and 3 SMQ terms and specific medical events included in these broad categories, and examine the effect of increasing IV LCM loading dose on the incidence of these select medical events. The study will also compare the incidence of the selected medical events in pediatric patient (aged  $\geq 1$  month  $< 17$  years) treated with higher IV LCM doses (including UCB's defined loading dose) to the incidence of these events in pediatric patients treated with a recommended initial/maintenance IV LCM dose.

The study will use electronic healthcare records (EHR) data from the PEDSnet data network, collected from the earliest (2009) through the latest date that data are available (~2018) for each included patient. The cohort design will allow the identification of pediatric patients treated with higher IV LCM doses or a recommended initial/maintenance IV LCM dose, and the ability to follow them to identify the occurrence of outcomes of interest.

[figure not shown]
The study will consist of two mutually exclusive cohorts. The first cohort will consist of pediatric patients treated with higher IV LCM doses (including UCB's defined loading dose).

The second, the comparator cohort will comprise of pediatric patients treated with recommended initial/maintenance IV LCM dose. The index date will be defined as the initiation of a new IV LCM treatment episode/receipt of a higher IV LCM dose than known maintenance dose (described in detail in Section 5.3.1). The exposure period will be defined as the time between the index date (as defined above) and discontinuation of IV LCM (described in more detail in Section 5.5.4). Demographic characteristics will be defined at the index date. Baseline data will be used to define clinical characteristics, LCM exposure indications and identify prevalent cases of the selected medical events of interest. Each subject will be followed from the index date up to 30 days after discontinuing treatment with IV LCM. During the follow-up period, data will be assessed for occurrence of the select medical events, defined in Section 5.5.5.

Outcome ascertainment will be performed in two ways. First, data elements within the PEDSnet common data model (CDM), which comprises structured data extracted from EHRs will be examined to identify the select medical events of interest. Each event will be defined using algorithms that will include diagnostic codes and if needed procedure and medication codes, recorded in the EHR. Second, because not all symptoms, signs, and health problems are included in the structured data as diagnosis codes, a chart review of the EHRs for all eligible study patients will be conducted to examine unstructured text data not captured in the CDM to identify additional patients with the select medical events of interest.

Patients with status epilepticus diagnostic codes in their record will be identified from the cohort and will have their results presented separately in sub tables. They will also contribute to the main study populations. This is to fulfill commitment to examine outcomes in SE patients when exposed to lacosamide. It is assumed that any patients treated with a loading dose of LCM will be more likely to be in SE and proving refractory to treatment than the usual seizure presentation in children.

**Figure 1 Schematic of the study design**

The index date will vary for each patient and will depend on when the patients fulfils the study criteria

## 5.2 Study population

The study population will consist of the following two mutually exclusive cohorts:

- Pediatric patients treated with higher IV LCM doses (including UCB's defined loading dose), regardless of diagnostic code i.e. patients do not have to have a formal diagnosis of specific types of epilepsy and they may include children with SE caused by other conditions.
- Pediatric patients treated with recommended initial/maintenance IV LCM dose regardless of diagnostic code i.e. patients do not have to have a formal diagnosis of specific types of epilepsy and they may include children with SE caused by other conditions.

These two groups are defined by the proposed alternative higher initial dosage (first dose, first treatment in observed episode) and the recommended initial dosage (first dose, first treatment in observed episode) and patients remain in that group thereafter. Switching is not allowed at any time.

Patients will be initially identified using the following study criteria.

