### • Study design, including data sources

#### *Study Design*

A retrospective cohort study will be conducted using data from the PEDSnet database to achieve the study objectives. Electronic health record (EHR) data will be collected from January 2009 to December 2018. Two mutually exclusive cohorts will be identified, the first

cohort consisting of pediatric patients treated with higher than the recommended IV LCM doses, and the second (comparator) cohort comprising pediatric patients treated with recommended initial/maintenance IV LCM dose. The index date will be defined as the initiation of a new IV LCM treatment episode/receipt of a higher IV LCM dose than known maintenance dose. The exposure period will be the period between the index date (as defined above) and discontinuation of LCM. Subjects will be followed from the index date up to 30 days after discontinuing treatment with LCM or censoring, and during this time will be assessed for occurrence of described study outcomes. All subjects require a baseline period prior to the index date free of either oral or IV LCM. In the stratified assessment of increasing LCM loading dose, follow up will be from the index date up to 24 hours and 7 days after discontinuing treatment with IV LCM. Outcome ascertainment will be done in two ways, 1) data elements within the PEDSnet common data model (CDM) will be examined to identify select medical events of interest; and 2) a chart review of the EHRs for all eligible study patients will be conducted to examine unstructured, text data not captured in the CDM to identify the select medical events of interest.

Patients with status epilepticus diagnostic codes in their record will be identified from the cohort and will have their results presented separately in sub tables. They will also contribute to the main study populations. This is to fulfill commitment to examine outcomes in SE patients when exposed to lacosamide.

- **Data analysis**

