### 5.2.1 Inclusion Criteria

- Patients with at least one iv LCM administration (earliest administration defines index date)
- At least 1 encounter with iv LCM administered between ages of  $\geq 1$  month and  $< 17$  years

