### 5.2.5 Dosing criteria for groups

Once the LCM population is identified dose thresholds are applied to define the “Recommended Dose Group” and the “Loading Dose Group”). The following thresholds apply:

The recommended loading dose groups are as follows:

- $< 4$  mg/kg for patients less than 30 kg and less than 6 months of age
- $< 6$  mg/kg for patients less than 30 kg and greater than or equal to 6 months of age
- $< 4$  mg/kg for patients between 30 and 50 kg
- $< 200$  mg for patients
- greater than 50 kg

Note: Whilst babies are allowed higher mg/kg dosing than older children, due to issues of metabolism and weight, babies under 6 months of age have immature organs and a loading dose should be lower than older babies under 1 year.

High dose group have doses greater than the recommended group cut limits, applicable for age and weight.

- $\geq 4$  mg/kg for patients less than 30 kg and less than 6 months of age
- $\geq 6$  mg/kg for patients less than 30 kg and greater than or equal to 6 months of age
- $\geq 4$  mg/kg for patients between 30 and 50 kg
- $\geq 200$  mg for patients greater than 50 kg

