### 5.3.3 Follow-up (post-index) period

The duration of follow-up is for a maximum of 37 days from index date.

IV LCM treatment may span several days; treatment will be considered continuous if subsequent IV LCM treatment is noted to occur within 7 days of a previous treatment. If 7 days pass without a documented iv or LCM treatment, the index exposure has ended. Follow then continues until end of follow up or until the following censoring conditions apply:

Censoring: Patients will be followed for either 37 days OR until the patient is lost to follow-up[transfer out]; OR the patient is discharged from the in-patient setting [events that occur at home are not easy to track and are not included here; outpatient setting events are also excluded as we do not know what the patient has been doing at home during routine care]; OR the patient dies; OR the patient switches to another AED instead of/or adjunct to LCM; whichever comes first.

Clarification of follow up: The purpose of the study is to evaluate iv loading dose and higher subsequent dosing risk. Some patients may receive only one iv loading dose and then transfer to oral dosing which may last some weeks in the hospital setting. In the case where a patient has just one dose of iv LCM and switches to continuous oral LCM therapy, the follow up for AE evaluation will cease after a maximum of seven days of oral therapy or until censoring occurs as above. The same applies for those exposed to one dose of iv LCM and no further LCM exposure (either oral or iv).

Patients who have more than one dose of iv LCM and then switch to oral therapy will have a maximum follow up of 37 days of follow up index date or until censoring.

Patient time is contributed until either end of follow up or censor point (in days).

Patients are only included once in this study, so if we find evidence of a further iv loading dose of LCM given 6 months later say, they do not contribute to the study.

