### **5.9.1.4 Sensitivity Analysis**

Sensitivity analyses will be conducted to assess parameters used for defining the selection criteria, exposure, outcomes, and the study period as indicated below:

- Shorten the baseline period to 6 weeks
- The follow-up time will not include the 30 days after discontinuation of IV LCM
- Exclude patients with preexisting medical events of interest
- Outcome definitions will include a code for an outcome related medication/procedure within the period following the diagnosis record (to be defined)

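### The dose group is fixed at the first dose, with no provision for comparator children who later receive an IV dose at or above the high-dose cut, and Sections 5.1 and 5.3.1 conflict with that rule

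*Protocol*

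**What the plan says.** - **Grouping.** Section 5.2 defines the groups by the first dose of the first treatment in the observed episode, and "patients remain in that group thereafter. Switching is not allowed at any time". In Section 5.2.1 the "earliest administration defines index date".
- **Cut.** Section 5.2.5 sets thresholds by age and weight: "High dose group have doses greater than the recommended group cut limits, applicable for age and weight". The list beneath includes doses equal to the limit.
- **Follow-up.** Section 5.3.3: "The duration of follow-up is for a maximum of 37 days from index date". Follow-up ends earlier at transfer out, discharge from the inpatient setting, death, or a change of antiepileptic drug: "OR the patient switches to another AED instead of/or adjunct to LCM; whichever comes first". A rise in the IV lacosamide dose is not listed.
- **Purpose.** Section 5.3.3: "The purpose of the study is to evaluate iv loading dose and higher subsequent dosing risk".
- **Sensitivity analyses.** Section 5.9.1.4 lists four: a shorter baseline period, exclusion of children with pre-existing events, a stricter outcome definition, and "The follow-up time will not include the 30 days after discontinuation of IV LCM".
- **A second index rule.** The executive summary and Section 5.1 also let the index date be set by a dose above the child's established maintenance dose. Section 5.3.1 gives this as a route into the high-dose cohort, and Section 5.3 selects that cohort first.

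**The concern.** The records are retrospective, so some children who began below the cut may have been escalated to a dose at or above it within the 37-day window. Section 5.1 assumes that children given a loading dose are more likely to be in refractory status epilepticus, so escalation after an inadequate first dose is plausible. An event after escalation is then charged to the recommended-dose group. In a safety study this error matters, because a dose-related harm would be reported as a smaller difference, or as none.

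The protocol's own reasoning points the same way. Section 15 explains that follow-up now stops at an added antiepileptic drug because attribution of a signal would otherwise be confounded. Crossing into the other exposure level raises a similar attribution question for the exposure under study, but the protocol makes no provision for it.

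**Working it through.** **Step 1: trace one child through the rules.** The first IV dose is below the 5.2.5 cut and a second IV dose, some days later, is at or above it. The child is still an inpatient and has no new antiepileptic drug.
- Index date (5.2.1): the first dose.
- Group (5.2): recommended dose, unchanged afterwards.
- Follow-up (5.3.3): continues, up to day 37.
- Counting (5.9.1.2): the first event after index counts, over all person-days at risk. An event after the second dose is therefore a comparator event.
- Sensitivity analyses (5.9.1.4): none addresses this. Dropping the 30 days after discontinuation does not help, because the crossing happens while treatment is under way.

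**Step 2: apply the other index rule.** Under 5.1 and 5.3.1 the second dose could set a high-dose index date, if it counts as exceeding an established maintenance dose. For that route 5.3.1 refers to Section 5.2, but the current 5.2 no longer describes it. The executive summary adds: "All subjects require a baseline period prior to the index date free of either oral or IV LCM". Section 5.2.2 sets this period at three months. A child already treated in the same episode cannot meet it. The route is written down but is undefined in 5.2 and blocked within an episode.

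**Step 3: can crossing occur inside the window?** As an illustration only, take the adult titration in the executive summary, a rise of 50 mg per dose each week. From 50 mg twice daily, a single dose reaches 200 mg after (200 − 50)/50 = 3 weeks, day 21, leaving 16 of 37 days. From 100 mg it takes 2 weeks, day 14, leaving 23 days. Crossing is possible by gradual titration, and earlier if the dose is raised faster.

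**Step 4: size.** The protocol gives no target IRR, event rate, power or group split. It gives only a feasibility count of 875 children before the full criteria and dose grouping (5.9.3), so there is no planned figure to reproduce. Let R be the true IRR and p the share of comparator person-days after crossing, with the post-crossing rate equal to the high-dose group's rate. Both R and p are assumptions.

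Observed IRR = R / ((1 − p) + pR)

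| True R | p = 0.05 | p = 0.10 | p = 0.20 |
|---|---|---|---|
| 1.5 | 1.46 | 1.43 | 1.36 |
| 2.0 | 1.90 | 1.82 | 1.67 |
| 3.0 | 2.73 | 2.50 | 2.14 |

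For example, R = 2 and p = 0.10 gives 2/(0.9 + 0.2) = 1.82.

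**Step 5: precision.** With equal person-time, two-sided 0.05 and 80% power (all assumed), events needed = 4(1.96 + 0.84)² / (ln IRR)². An IRR of 2.0 needs 66 events. The diluted values 1.82 and 1.67 need 88 and 121. With 66 events, power falls from 80% to 68% at p = 0.10 and 55% at p = 0.20.

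**The case against.** **First-dose grouping is legitimate.** It compares initial-dose strategies, and later increases may be part of such a strategy. The parallel with an added drug is therefore imperfect. This stands, and it is why the primary rule should stay.

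**The protocol is not silent on later high doses.** A reader might infer that nothing at all happens when a child later receives one. The documents do not support that, because 5.1 and 5.3.1 contain a rule for a dose above maintenance and 5.3 selects the high-dose cohort first. What they show is two rules that conflict, the second of which cannot operate within an episode.

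**Later dosing is not wholly invisible.** A reader might also infer that the study cannot see later dosing risk anywhere. That goes too far. Later doses in children who started high are followed, and the executive summary plans, if numbers permit, a stratum for first versus multiple loading-dose exposures. That stratum does not fill the gap, since a child who started low and had one later high dose has had only one such exposure.

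**The switching sentence.** It need not be read as an instruction to clinicians. Its natural sense is no analytic reassignment. It could also be read as excluding such children, so it should be made explicit.

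**The share p may be small.** Discharge and an added antiepileptic drug both end follow-up, and refractory children may well receive another drug. Large values of p are unlikely. Against this, 5.3.3 stops follow-up after at most seven days for children with a single IV dose, while those with several may run to day 37. Children who can cross are among those with the longest permitted follow-up. Section 5.9.4 also expects most events within 24 hours of IV lacosamide, so a person-time share is only a crude guide to how many events are misattributed.

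**Such analyses are often left to the SAP.** The SAP is not shown and may include one. The grouping rule, the censoring list, the stated purpose and the conflicting index rule are all in the protocol, however.

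**Conclusion.** The concern holds in a limited form. Under Sections 5.2, 5.2.1, 5.3.3 and 5.9.1.2, events after a comparator child's later dose at or above the cut are counted in the recommended-dose group. No listed sensitivity analysis shows how much this matters. If higher doses cause harm, the bias is towards an IRR of 1. The main comparison does not isolate later high-dose risk in children who started low. Separately, Sections 5.1 and 5.3.1 contradict 5.2 and 5.2.1 on whether a later higher dose can set the index date.

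The size cannot be established from the protocol. Over p from 0.05 to 0.20, a true IRR of 2.0 would appear as 1.90 to 1.67. This assumes constant rates and a post-crossing rate equal to that of children who started high. If few children cross, the effect is negligible, and reporting the crossings would show that. This is an improvement that should be made; it does not invalidate the design.

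**What to change.** 1. Keep first-dose classification as the primary analysis.
2. Add to Section 5.9.1.4 a sensitivity analysis that censors comparator children at their first later IV lacosamide dose at or above the existing 5.2.5 cut for their age and weight.
3. Report the number of children who cross and when, and tabulate their post-crossing events in a separate row.
4. Reword the switching sentence in 5.2 to say that the group is not changed by later doses.
5. Reconcile 5.1, 5.2, 5.2.1 and 5.3.1, with the matching executive summary text, so that one rule for index date and group applies. Which clinical dose rule should hold is not a matter for this review.

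The cost is one extra analysis and one descriptive row. Section 5.5.4 already anticipates time-stamped doses and the identification of later loading-dose episodes. The downside is that censoring at escalation may be informative and may remove increases that belong to the initial-dose strategy, so the analysis is supportive only.

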### 5.2.1 Inclusion Criteria

- Patients with at least one iv LCM administration (earliest administration defines index date)
- At least 1 encounter with iv LCM administered between ages of  $\geq 1$  month and  $< 17$  years

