### 5.2.2 Exclusion Criteria

- No exposure to either oral or iv LCM within the 3 months prior to the index date
  - In the case of patients  $< 90$  days of age, no prior LCM ever in the record

A separate cohort for patients  $< 30$  days old is established with the following criteria.

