### 5.2.3 Neonates Inclusion Criteria

- Patients with at least one iv LCM administration (earliest administration defines index date)
- At least 1 encounter with iv LCM administered before 30 days of age.

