### 5.2.4 Neonates exclusion criteria

- No exposure to either oral or iv LCM prior to the index date

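### Section 5.2.1 ties the age range to any IV lacosamide encounter and not to the index date, so a neonate re-dosed at 1 month or older meets the main-cohort criteria with an index below the stated age

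*Protocol*

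**What the plan says.** Section 5.2.1 gives the main cohort two inclusion criteria. The first is "Patients with at least one iv LCM administration (earliest administration defines index date". The second begins "At least 1 encounter with iv LCM administered between ages of" and gives the range of 1 month to under 17 years. Neither mentions age at the index date.

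Section 5.2.2 adds the washout, "No exposure to either oral or iv LCM within the 3 months prior to the index date". For patients under 90 days of age it becomes no earlier LCM at all. The same section then announces "A separate cohort for patients" under 30 days old. Its criteria, in 5.2.3 and 5.2.4, use the same earliest-dose index, require "At least 1 encounter with iv LCM administered before 30 days of age", and set the washout "No exposure to either oral or iv LCM prior to the index date".

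Section 5.2 assigns the dose group from the first dose of the observed episode and forbids switching. Section 5.3.3 limits follow-up to 37 days from the index and states "Patients are only included once in this study". Section 5.3.1 defines the index in another way, as the earliest qualifying episode or dose in the study period with the required baseline. The note under Figure 1 says the index depends on when the patient meets the criteria.

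**The concern.** The stated population is children aged 1 month to under 17 years (section 5.1 and the first secondary objective in the executive summary). As worded, the entry rule lets a dose given before 1 month serve as the index in that population, provided some later IV dose falls in range. Three things are at stake.

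- **Exposure and follow-up.** Dose group, baseline and person-time are all anchored at the neonatal dose. The dose that made the child eligible may fall outside follow-up altogether.
- **Conditioning on the future.** A child first dosed as a neonate enters the main cohort only by surviving and being dosed again later. The time in between is immortal. Section 15 explains that a requirement for 37 days of activity was dropped because it favoured healthy survivors; this wording brings back a limited version of that problem.
- **Cohort membership.** The same child satisfies the neonatal criteria. Section 15 adds neonates because safety data are lacking and dosing regimens are unknown in them, so keeping the two populations apart matters to the plan's own logic.

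**Working it through.** The protocol states no figure on this point, so there is nothing to reproduce. The check applies the rules of 5.2.1 to 5.2.4 to hypothetical dosing histories.

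**Rules applied**
- Index = earliest IV LCM dose (5.2.1, 5.2.3).
- Main cohort: at least one IV dose at 1 month or older and under 17 years, and no LCM in the 3 months before the index, or ever before it if the index age is under 90 days (5.2.1, 5.2.2). One month is taken as 30.4 days, which is an assumption.
- Neonatal cohort: at least one IV dose before 30 days and no LCM before the index (5.2.3, 5.2.4).

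**Rules as written**

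| IV doses at age | Main criteria met | Neonatal criteria met | Index age |
|---|---|---|---|
| Day 10 only | no | yes | 10 days |
| Days 10 and 12 | no | yes | 10 days |
| Days 28, 31 and 33, one stay | yes | yes | 28 days |
| Days 10 and 60 | yes | yes | 10 days |
| Days 10 and 150 | yes | yes | 10 days |
| Day 10 and 3 years | yes | yes | 10 days |
| 5 years only | yes | no | 5 years |

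The washout never acts on these children. The index is the earliest IV dose and these histories contain no other LCM, so nothing precedes it.

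**Effect on follow-up.** With an index at day 10, follow-up ends by day 10 + 37 = day 47 at the latest. In the histories with a second dose at day 60, day 150 or 3 years, the qualifying dose comes after that, so the child is certain to be alive throughout follow-up. With an index at day 28 the limit is day 28 + 37 = day 65, so the in-range doses at days 31 and 33 fall inside the window but do not set the index or the dose group.

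**Only the lower age bound is exposed.** If any dose is before 17 years, the earliest dose is too, so the index cannot be too old.

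**Two possible repairs, on the same histories**
- *A: age at the earliest dose must be in range.* All four overlapping histories leave the main cohort and stay only in the neonatal cohort.
- *B: index = first IV dose in the age range, with the washout applied there.* The day 28–33 stay and days 10 and 60 fail the main criteria. Days 10 and 150, and day 10 and 3 years, enter with an in-range index but still meet the neonatal criteria. B cures the out-of-range index but not the overlap.

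**The case against.** The best defence is that the intent is clear from the rest of the protocol. Section 5.1 states the age range and defines demographics at the index date, and 5.5.3 lists age at the index date. Under 5.3.1 or the Figure 1 note, the index might be the first in-range dose. The child dosed on days 10 and 60 would then fail the washout, and the child dosed on days 10 and 150 would have an in-range index. This shows the likely intent, but it does not settle the rule. Those places conflict with the explicit earliest-dose definition in 5.2.1, and nothing says which governs. Section 5.3.1 sets no age limit on the index either, and 5.3.2 allows a birth-to-index baseline for infants under 3 months.

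A reader might infer more than the documents support:
- *That all children first dosed as neonates are affected.* They are not. A child dosed only before 30 days meets the neonatal criteria alone.
- *That affected children are certainly counted twice.* Section 5.3.3 allows one inclusion per patient. What exists is an overlap in criteria that conflicts with that rule, with no order of precedence. The one-cohort statement in 5.3 is written for the two dose cohorts and does not settle the neonatal question.
- *That the index is out of range in both cohorts.* It is in range for the neonatal cohort.
- *That a given share of the youngest age band is contaminated.* Section 5.9.1.3 calls for tables by age band, but the protocol does not define the bands.

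**Conclusion.** The point holds as a faulty eligibility rule. On the wording of 5.2.1 to 5.2.4, a child given IV LCM before 30 days and again at 1 month or older meets the main-cohort criteria with an index below the stated age range, and meets the neonatal criteria as well. The competing index definitions in 5.3.1 and under Figure 1 add a contradiction and do not cure the problem. Two careful programmers could build different cohorts from this text.

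The size is unknown. The 875 patients in section 5.9.3 are a feasibility count with no breakdown by age at first dose or by re-dosing, so any percentage would be a guess. The number may be small, and no effect on an overall incidence rate ratio has been shown. The conclusion rests on the literal text; the 30.4-day month affects only cases close to the boundary. The mismatch between under 30 days in one cohort and 1 month in the other could also leave out a child whose only dose falls on day 30, which is trivial and disappears with the same repair.

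**What to change.** - In 5.2.1, put the age condition on the index administration: at least 30 days and under 17 years at index. In 5.2.3, require under 30 days at index. Use days for the lower boundary throughout.
- State that the neonatal and main cohorts are mutually exclusive, and that a child indexed as a neonate belongs only to the neonatal cohort.
- Align 5.2.1, 5.3.1 and the note under Figure 1 to one index definition.

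This is repair A with an explicit precedence rule. Indexing at the first in-range dose is a possible alternative, but it would need its own precedence rule because some children would still meet both sets of criteria. The cost is a few sentences and a simple programming filter. The downside is that a few children leave the main cohort.
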